10.12.8.8. Adverse Events, Serious Adverse Events, and Other Safety Reporting for Substudy B

See Section 8.4.

10.12.8.9. Study Procedures for Substudy B

10.12.8.9.1. Screening (0 to 28 Days Before Visit 201) for Substudy B

Before enrollment and before any study-related procedures are performed, voluntary, written, study-specific informed consent will be obtained from the participant. Each signature on the ICD must be personally dated by the signatory. The investigator or his or her designee will also sign the ICD. A copy of the signed and dated ICD must be given to the participant. The source data must reflect that the informed consent was obtained before participation in the study.

It is anticipated that the procedures below will be conducted in a stepwise manner

- Assign a participant number using the IRT system.
- Obtain the participant's demography (including date of birth, sex, race, and ethnicity).
 The full date of birth will be collected to critically evaluate the immune response and safety profile by age.
- Obtain medical history, including confirmed COVID-19 diagnosis (see Section 8.4.7) or asymptomatic positive SARS-CoV-2 test result (NAAT or antigen test), and any other medical history of clinical significance.
- Obtain the details of any medications currently taken.
- Perform 12-lead triplicate ECG.
- Perform physical examination, including vital signs (weight, height, oral temperature, pulse rate, and seated blood pressure), evaluating any clinically significant abnormalities within the following body systems: general appearance; skin; head, eyes, ears, nose, and throat; heart; lungs; abdomen; musculoskeletal; extremities; neurological; and lymph nodes.

- Collect a blood sample of approximately 2.5 mL as detailed in the laboratory manual for troponin I laboratory testing as described in Section 8.3.4.
- Perform urine pregnancy test on WOCBP as described in Section 8.3.6.
- Discuss contraceptive use as described in Section 5.3.1.
- Record nonstudy vaccinations as described in Section 10.12.6.7.
- Review documentation of all prior COVID-19 vaccinations. All vaccines must be authorized for use in the US. Record prior receipt of any COVID-19 vaccine as described in Section 10.12.6.7.
- Record prior receipt of any pneumococcal vaccine as described in Section 10.12.6.7.
- Record details of any licensed influenza vaccine received in the prior 12 months, as described in Section 10.12.6.7.
- Ensure and document that all of the inclusion criteria and none of the exclusion criteria are met.
- Record AEs as described in Section 8.4.1.
- The investigator or an authorized designee completes the CRF.

10.12.8.9.2. Visit 201 – Vaccination (Day 1) for Substudy B

- It is anticipated that the procedures below will be conducted in a stepwise manner.
- Discuss contraceptive use as described in Section 5.3.1.
- Record nonstudy vaccinations as described in Section 10.12.6.7.
- Review screening central laboratory results (troponin I) and central ECG reports.
- Perform 12-lead triplicate ECG.
- Perform a clinical assessment. If the clinical assessment indicates that a physical
 examination is necessary to comprehensively evaluate the participant, perform a physical
 examination and record any findings in the source documents and, if clinically
 significant, record on the medical history CRF or on the AE CRF as per Section 10.3.
- Measure vital signs, including oral temperature, pulse rate, and seated blood pressure.
- Perform urine pregnancy test on WOCBP as described in Section 8.3.6.

- Ensure that the participant continues to meet all of the inclusion criteria and none of the exclusion criteria.
- Ensure that the participant meets none of the temporary delay criteria as described in Section 5.5.
- Obtain the participant's randomization number and study intervention allocation using the IRT system.
- Collect a blood sample of approximately 2.5 mL as detailed in the laboratory manual for troponin I laboratory testing as described in Section 8.3.4.
- Collect a blood sample (approximately 15 mL or 50 mL), before administration of study intervention, for immunogenicity assessment.
- Site staff member(s) will dispense/administer 1 dose of study intervention into the deltoid muscle per Section 10.12.6.1.1.
- Site staff must observe the participant for at least 30 minutes after study intervention administration for any acute reactions. Record any acute reactions (including time of onset) in the participant's source documents and on the AE page of the CRF, and on an SAE form as applicable.
- Issue a measuring device to measure local reactions at the injection site and a thermometer for recording daily temperatures and provide instructions on their use.
- Explain the e-diary completion requirement to the participant and assist the participant
 with downloading the study application onto the participant's own device or issue a
 provisioned device if required. Provide instructions on e-diary completion and ask the
 participant to complete the reactogenicity e-diary from Day 1 through Day 7, with Day 1
 being the day of vaccination.
- Ask the participant to contact the site staff or investigator immediately if he or she
 experiences any of the following from Day 1 through Day 7 after vaccination
 (where Day 1 is the day of vaccination) to determine if an unscheduled reactogenicity
 visit is required:
 - Fever ≥39.0°C (≥102.1°F).
 - Redness or swelling at the injection site measuring greater than 10 cm (>20 measuring device units).
 - Severe pain at the injection site.
 - Any severe systemic event.

- Record AEs as described in Section 8.4.1.
- Ask the participant to contact the site staff or investigator if a medically attended event (eg, doctor's visit, emergency room visit) or hospitalization occurs.
- Ask the participant to contact the site staff or investigator immediately if the participant experiences acute chest pain, shortness of breath, or palpitations (see Section 10.12.8.10).
- Schedule an appointment for the participant to return for the next study visit.
- Remind the participant to bring the e-diary to the next visit.
- Complete the source documents.
- The investigator or an authorized designee completes the CRFs and updates the study intervention accountability records.
- The investigator or appropriately qualified designee reviews the reactogenicity
 e-diary data online following vaccination to evaluate participant compliance and as part
 of the ongoing safety review. Daily review is optimal during the active diary period.

10.12.8.9.3. Visit 202 – Day 3 Follow-Up Visit (After Vaccination) – 2 to 4 Days After Visit 201 for Substudy B

- Record AEs as described in Section 8.4.1.
- Record nonstudy vaccinations as described in Section 10.12.6.7.
- Record prohibited medication use as described in Section 10.12.6.7.1.
- Verify understanding of and compliance with protocol requirements for contraception as described in Section 5.3.1.
- Review screening central laboratory results (troponin I) and central ECG reports. Any abnormal troponin I level must result in further assessments as outlined in Section 10.12.8.10.
- Perform 12-lead triplicate ECG. Any new ECG abnormality (compared to baseline) consistent with probable or possible myocarditis or pericarditis (as listed in Section 10.12.8.5.1) must result in further assessments as outlined in Section 10.12.8.10.
- Measure vital signs, including oral temperature, pulse rate, and seated blood pressure.
- Collect a blood sample of approximately 2.5 mL as detailed in the laboratory manual for troponin I laboratory testing as described in Section 8.3.4.

- Remind the participant to contact the site staff or investigator immediately if he or she
 experiences any of the following from Day 1 through Day 7 after vaccination
 (where Day 1 is the day of vaccination) to determine if an unscheduled reactogenicity
 visit is required:
 - Fever ≥39.0°C (≥102.1°F).
 - Redness or swelling at the injection site measuring greater than 10 cm (>20 measuring device units).
 - Severe pain at the injection site.
 - Any severe systemic event.
- Remind the participant to contact the site staff or investigator if a medically attended event (eg, doctor's visit, emergency room visit) or hospitalization occurs.
- Remind the participant to contact the site staff or investigator immediately if the
 participant experiences acute chest pain, shortness of breath, or palpitations
 (see Section 10.12.8.10).
- Remind the participant to complete the e-diary, which should be reviewed daily by the site
- Schedule an appointment for the participant to return for the next study visit.
- Complete the source documents.
- The investigator or an authorized designee completes the CRFs.

10.12.8.9.4. Visit 203 – 1-Week Follow-Up Visit (After Vaccination) – 6 to 8 Days After Visit 201 for Substudy B

- Record AEs as described in Section 8.4.1.
- Record nonstudy vaccinations as described in Section 10.12.6.7.
- Record prohibited medication use as described in Section 10.12.6.7.1.
- Verify understanding of and compliance with protocol requirements for contraception as described in Section 5.3.1.
- Review screening central laboratory results (troponin I) and central ECG reports. Any abnormal troponin I level must result in further assessments as outlined in Section 10.12.8.10.

- Perform 12-lead triplicate ECG. Any new ECG abnormality (compared to baseline) consistent with probable or possible myocarditis or pericarditis (as listed in Section 10.12.8.5.1) must result in further assessments as outlined in Section 10.12.8.10.
- Measure vital signs, including oral temperature, pulse rate, and seated blood pressure.
- Collect a blood sample of approximately 2.5 mL as detailed in the laboratory manual for troponin I laboratory testing as described in Section 8.3.4.
- Review the participant's reactogenicity e-diary data. If the e-diary collection period is complete:
 - Collect stop dates of any reactogenicity e-diary events ongoing on the last day that the reactogenicity e-diary was completed and record stop dates in the CRF if required.
 - Collect the participant's e-diary or assist the participant with removing the study application from his or her own personal device (if the visit is conducted after Day 7).
- Remind the participant to contact the site staff or investigator immediately if he or she
 experiences any of the following from Day 1 through Day 7 after vaccination
 (where Day 1 is the day of vaccination) to determine if an unscheduled reactogenicity
 visit is required:
 - Fever ≥39.0°C (≥102.1°F).
 - Redness or swelling at the injection site measuring greater than 10 cm (>20 measuring device units).
 - Severe pain at the injection site.
 - Any severe systemic event.
- Remind the participant to contact the site staff or investigator if a medically attended event (eg, doctor's visit, emergency room visit) or hospitalization occurs.
- Remind the participant to contact the site staff or investigator immediately if the participant experiences acute chest pain, shortness of breath, or palpitations (see Section 10.12.8.10).
- Schedule an appointment for the participant to return for the next study visit.
- Complete the source documents.
- The investigator or an authorized designee completes the CRFs.

10.12.8.9.5. Visit 204 – 4-Week Follow-Up Visit (After Vaccination) – 26 to 30 Days After Visit 201 for Substudy B

- Record AEs as described in Section 8.4.1.
- Record nonstudy vaccinations as described in Section 10.12.6.7.
- Record prohibited medication use as described in Section 10.12.6.7.1.
- Verify understanding of and compliance with protocol requirements for contraception as described in Section 5.3.1.
- Review screening central laboratory results (troponin I) and central ECG reports. Any abnormal troponin I level must result in further assessments as outlined in Section 10.12.8.10.
- Collect a blood sample of approximately 15 mL or 50 mL for immunogenicity testing.
- Review the participant's reactogenicity e-diary data. Collect stop dates of any
 reactogenicity e-diary events ongoing on the last day that the reactogenicity e-diary was
 completed and record stop dates in the CRF if required.
- If not already completed, collect the participant's e-diary or assist the participant with removing the study application from his or her own personal device.
- Record any AEs that occur within the 48 hours after the blood draw as described in Section 8.4.1.

10.12.8.9.6. Visit 205 – 6-Month Telephone Contact – 175 to 189 Days After Last Study Vaccination for Substudy B

- Contact the participant by telephone.
- Record SAEs as described in Section 8.4.1.
- Record nonstudy vaccinations as described in Section 10.12.6.7.
- Record prohibited medication use as described in Section 10.12.6.7.1.
- Complete the source documents.
- The investigator or an authorized designee completes the CRFs.

10.12.8.9.7. Unscheduled Visit for a Grade 3 or Suspected Grade 4 Reaction for Substudy B

If a Grade 3 local reaction (Section 8.3.5.2), systemic event (Section 8.3.5.3), or fever (Section 8.3.5.4) is reported in the reactogenicity e-diary, a telephone contact should occur to ascertain further details and determine whether a site visit is clinically indicated. If a suspected Grade 4 local reaction (Section 8.3.5.2), systemic event (Section 8.3.5.3), or fever (Section 8.3.5.4) is reported in the reactogenicity e-diary, a telephone contact or site visit should occur to confirm whether the event meets Grade 4 criteria.

A site visit must be scheduled as soon as possible to assess the participant unless any of the following is true:

- The participant is unable to attend the unscheduled visit.
- The local reaction/systemic event is no longer present at the time of the telephone contact.
- The participant recorded an incorrect value in the reactogenicity e-diary (confirmation of a reactogenicity e-diary data entry error).
- The PI or authorized designee determined it was not needed.

This telephone contact will be recorded in the participant's source documentation and the CRF.

If the participant is unable to attend the unscheduled visit, or the PI or authorized designee determined it was not needed, any ongoing local reactions/systemic events must be assessed at the next study visit.

During the unscheduled visit, the reactions should be assessed by the investigator or a medically qualified member of the study staff, such as a study physician or a study nurse, as applicable to the investigator's local practice, who will:

- Measure body temperature (°F/°C).
- Measure minimum and maximum diameters of redness (if present).
- Measure minimum and maximum diameters of swelling (if present).
- Assess injection site pain (if present) in accordance with the grades provided in Section 8.3.5.2.
- Assess systemic events (if present) in accordance with the grades provided in Section 8.3.5.3.

- Assess other findings associated with the reaction and record this on the AE page of the CRF if appropriate.
- The investigator or an authorized designee will complete the unscheduled visit assessment page of the CRF.

10.12.8.10. Additional Procedures for Monitoring of Potential Myocarditis or Pericarditis for Substudy B

Any study participant who reports acute chest pain, shortness of breath, palpitations, or any other symptom(s) that might be indicative of myocarditis or pericarditis within 6 weeks after study vaccination must be specifically evaluated in clinic by a cardiologist for possible myocarditis or pericarditis. The same applies for any participant in whom a new ECG abnormality (compared to baseline) consistent with probable or possible myocarditis or pericarditis (as listed in Section 10.12.8.5.1) or abnormal troponin I level is observed at Visit 202 or Visit 203.

In addition to a clinical evaluation, the following should be performed:

- ECG and
- Measurement of the troponin level

For any participant in whom a new ECG abnormality (compared to baseline) consistent with probable or possible myocarditis or pericarditis (as listed in Section 10.12.8.5.1) or abnormal troponin I level is observed at Visit 202 or Visit 203, this should be achieved by repeating the assessments with the central vendor(s).

If myocarditis or pericarditis is suspected based upon the initial evaluation, the following should also be performed:

- Cardiac echocardiogram and/or
- Cardiac magnetic resonance study

Details of the symptoms reported, and results of the investigations performed, will be recorded in the CRF.

Any diagnosis of myocarditis or pericarditis is considered an important medical event and must be reported as an SAE (refer to Sections 8.4.1.1 and 8.4.3). Other diagnoses should be recorded as AEs or SAEs, as appropriate. Refer also to Section 8.4.7.

10.12.8.11. Additional Procedures for Monitoring of Potential Menstrual Cycle Disturbances for Substudy B

Any female study participant who reports any symptoms that may indicate a disturbance of their normal menstrual cycle (including, but not exclusively, heavy menstrual bleeding, amenorrhea, and irregular periods) following receipt of study intervention until 6 months after the first vaccination should be specifically evaluated by the investigator. Details of the symptoms, menstrual history, and results of any investigations performed will be recorded in the CRF.

10.12.8.11.1. Unscheduled Visit for a Grade 3 or Suspected Grade 4 Reaction for Substudy B

If a Grade 3 local reaction (Section 8.3.5.2), systemic event (Section 8.3.5.3), or fever (Section 8.3.5.4) is reported in the reactogenicity e-diary, a telephone contact should occur to ascertain further details and determine whether a site visit is clinically indicated. If a suspected Grade 4 local reaction (Section 8.3.5.2), systemic event (Section 8.3.5.3), or fever (Section 8.3.5.4) is reported in the reactogenicity e-diary, a telephone contact or site visit should occur to confirm whether the event meets Grade 4 criteria.

A site visit must be scheduled as soon as possible to assess the participant unless any of the following is true:

- The participant is unable to attend the unscheduled visit.
- The local reaction/systemic event is no longer present at the time of the telephone contact.
- The participant recorded an incorrect value in the reactogenicity e-diary (confirmation of a reactogenicity e-diary data entry error).
- The PI or authorized designee determined it was not needed.
- This telephone contact will be recorded in the participant's source documentation and the CRF.

If the participant is unable to attend the unscheduled visit, or the PI or authorized designee determined it was not needed, any ongoing local reactions/systemic events must be assessed at the next study visit.

During the unscheduled visit, the reactions should be assessed by the investigator or a medically qualified member of the study staff, such as a study physician or a study nurse, as applicable to the investigator's local practice, who will:

- Measure oral temperature (°F/°C).
- Measure minimum and maximum diameters of redness (if present).

- Measure minimum and maximum diameters of swelling (if present).
- Assess injection site pain (if present) in accordance with the grades provided in Section 8.3.5.2.
- Assess systemic events (if present) in accordance with the grades provided in Section 8.3.5.3.
- Assess for other findings associated with the reaction and record these on the AE page of the CRF if appropriate.
- The investigator or an authorized designee will complete the unscheduled visit assessment page of the CRF.

10.12.8.12. Additional Procedures for Monitoring of Potential Myocarditis or Pericarditis for Substudy B

During Substudy B, participants 18 through 64 years of age will be closely monitored for potential asymptomatic and symptomatic myocarditis/pericarditis, including the use of routine ECGs and troponin testing.

Any study participant who reports acute chest pain, shortness of breath, palpitations, or any other symptom(s) that might be indicative of myocarditis or pericarditis within 6 weeks after study vaccination must be specifically evaluated in clinic by a cardiologist for possible myocarditis or pericarditis:

- Acute chest pain,
- Shortness of breath,
- Palpitations, or
- Any other symptom(s) that might be indicative of myocarditis or pericarditis.
- In addition to a clinical evaluation, the following should be performed:
- ECG and
- Measurement of the troponin level.

If myocarditis or pericarditis is suspected based upon the initial evaluation, the following should also be performed:

- Cardiac echocardiogram and/or
- Cardiac magnetic resonance study.

Details of the symptoms reported, and results of the investigations performed, will be recorded in the CRF. Any diagnosis made (eg, myocarditis, pericarditis, or other) should be recorded as an AE or SAE, as appropriate. Refer also to Section 8.4.7.

10.12.8.13. Additional Procedures for Monitoring of Potential Menstrual Cycle Disturbances for Substudy B

Any female study participant who reports any symptoms that may indicate a disturbance of their normal menstrual cycle (including, but not exclusively, heavy menstrual bleeding, amenorrhea, and irregular periods) following receipt of study intervention until 6 months after the first vaccination should be specifically evaluated by the investigator at the next planned visit. Details of the symptoms, menstrual history, and results of any investigations performed will be recorded in the CRF.

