This vaccine has the same modRNA platform (with sequence changes limited to those that are Omicron-specific) and LNP formulation as BNT162b2; therefore, the safety profile is expected to be similar to that of BNT162b2, ie, local reactions, such as injection site redness, injection site swelling, and injection site pain, and systemic events, such as fever, fatigue, headache, chills, vomiting, diarrhea, muscle pain, and joint pain. Other key risks identified for BNT162b2 are lymphadenopathy; hypersensitivity reactions, such as rash, pruritus, urticaria, angioedema, and anaphylaxis; and myocarditis and pericarditis.	These are common adverse reactions seen with other vaccines as well as the COVID-19 vaccine. Data available from the C4591001 study (with BNT162b2) showed low incidence of severe or serious events and no clinically concerning safety observations across the safety population and within demographic subgroups based on age, sex, race/ethnicity, country, and baseline SARS-CoV-2 status. 1-Week follow-up reactogenicity data of 194 participants who received mIRV, bIRV, or qIRV in C4781001 Substudy A and 120 participants from C4781001 Substudy B showed most events to be mild to moderate in severity, with the most common events being pain at the injection site, fatigue, and headache. Anaphylaxis: Frequency not known.	and SAEs through 6 months after Visit 1/201. Specific reference to these risks is made within the ICD, with instruction to contact a healthcare professional if a case is suspected. For anaphylaxis, there is an on-site 30-minute
	Myocarditis and pericarditis: Very rare cases of myocarditis and pericarditis have been reported following vaccination with modRNA SARS-CoV-2 vaccines after authorization. Typically, the cases have occurred more often in younger men and after the second dose of the vaccine and within 14 days after vaccination. These are generally mild cases, and individuals tend to recover within a short time	observation period after vaccination. Instructions for handling suspected cases of myocarditis and pericarditis are found in Section 10.11.8.8.10 and Section 10.12.8.12.

Potential Risk of Clinical Significance	Summary of Data/Rationale for Risk	Mitigation Strategy				
	following standard treatment and rest. Healthcare professionals should be alert to the signs and symptoms of myocarditis and pericarditis in vaccine recipients.					

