8.4.1.1. Reporting SAEs to Pfizer Safety

All SAEs occurring in a participant during the active collection period as described in Section 8.4.1 are reported to Pfizer Safety on the Vaccine SAE Report Form immediately upon awareness and under no circumstance should this exceed 24 hours, as indicated in Appendix 3. The investigator will submit any updated SAE data to the sponsor within 24 hours of its being available.

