8.4.7. Adverse Events of Special Interest

The following events are considered AESIs:

For Substudy A:

- A confirmed diagnosis of influenza.
- Confirmed diagnosis of myocarditis or pericarditis occurring within 4 weeks after vaccination. See Section 10.11.8.8.10.
- Confirmed COVID-19 diagnosis after Visit 1 through the end of the study (clinical signs/symptoms per CDC²⁸ and positive SARS-CoV-2 NAAT or rapid antigen test result).

For Substudy B:

- A confirmed diagnosis of influenza.
- Confirmed diagnosis of myocarditis or pericarditis occurring within 6 weeks after vaccination. See Section 10.12.8.12.
- Confirmed COVID-19 diagnosis after Visit 201 through the end of the study (clinical signs/symptoms per CDC²⁸ and positive SARS-CoV-2 NAAT or rapid antigen test result) (excluding Group 12).
- Potential menstrual cycle disturbances. See Section 10.12.8.11.

AESIs are examined as part of routine safety data review procedures throughout the clinical trial and as part of signal detection processes. Should an aggregate analysis indicate that these prespecified events occur more frequently than expected, eg, based on epidemiological data, literature, or other data, then this will be submitted and reported in accordance with Pfizer's safety reporting requirements. Aggregate analyses of safety data will be performed on a regular basis per internal SOPs.

All AESIs must be reported as an AE or SAE following the procedures described in Section 8.4.1 through 8.4.4. An AESI is to be recorded as an AE or SAE on the CRF. In addition, an AESI that is also an SAE must be reported using the Vaccine SAE Report Form.

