10.12.8.5.1. ECGs for Substudy B

ECGs will be collected at the times specified in Section 10.12.1 for Substudy B.

All scheduled 12-lead ECGs should be performed after the participant has rested quietly for at least 10 minutes in a supine position. The ECGs should be obtained prior to blood collection, measurement of blood pressure, and measurement of pulse rate. ECGs will be performed in triplicate.

ECG data will be submitted to a central laboratory for evaluation. The final ECG report from the central laboratory should be maintained in the participant's source documentation and be the final interpretation of the ECG recording. Any clinically significant changes from the baseline/Day 1 ECG may potentially be AEs (see Section 10.3) and should be evaluated further, as clinically warranted.

In some cases, it may be appropriate to repeat abnormal ECGs to rule out improper lead placement as contributing to the ECG abnormality. It is important that lead placement be in the same position each time during each assessment visit in order to achieve precise ECG recordings.

ECG abnormalities consistent with probable or possible myocarditis or pericarditis are those judged as such by a cardiologist, including:

- Sustained atrial or ventricular arrhythmias
- Second-degree Mobitz Type II or worse AV block, new bundle branch block
- Diffuse ST-segment elevation or PR-segment inversion, compatible with pericarditis

Echocardiograms may be performed as detailed in Section 10.12.8.10.

ECG values of potential clinical concern are listed in Section 10.9.

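### Substudy B has two same-titled myocarditis/pericarditis sections with different seriousness rules, and the AESI and risk sections cite only the permissive one

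*Protocol*

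**What the plan says.** Protocol Appendix 12 contains two sections, 10.12.8.10 and 10.12.8.12, both titled as additional monitoring procedures for potential myocarditis or pericarditis in Substudy B. Both are current Amendment 6 text.

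- Section 10.12.8.10: "Any diagnosis of myocarditis or pericarditis is considered an important medical event and must be reported as an SAE". It leaves investigator judgement on seriousness for other diagnoses only.
- Section 10.12.8.12: "Any diagnosis made (eg, myocarditis, pericarditis, or other) should be recorded as an AE or SAE, as appropriate".

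Other sections divide between the two:

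- Section 8.4.7, AESIs for Substudy B: "Confirmed diagnosis of myocarditis or pericarditis occurring within 6 weeks after vaccination. See Section 10.12.8.12".
- Section 2.3.1, risk table: "Instructions for handling suspected cases of myocarditis and pericarditis are found in Section 10.11.8.8.10 and Section 10.12.8.12". The first of these is the Substudy A section.
- Section 10.12.8.5.1, ECGs: "Echocardiograms may be performed as detailed in Section 10.12.8.10".
- Sections 10.12.8.9.2 to 10.12.8.9.5 (Visits 201 to 204) cite 10.12.8.10 for further assessment: for cardiac symptoms at Visits 201 to 203, for abnormal troponin at Visits 202 to 204, and for new ECG findings at Visits 202 and 203.

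On reporting, Section 8.4.7 adds that "an AESI that is also an SAE must be reported using the Vaccine SAE Report Form". Section 8.4.1.1 requires SAEs to reach the sponsor "immediately upon awareness and under no circumstance should this exceed 24 hours".

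**The concern.** Myocarditis and pericarditis are key identified risks of this vaccine platform, and Substudy B schedules ECGs and troponin tests to look for them. Section 10.12.8.10 shows that the sponsor wanted no discretion about their seriousness. Section 10.12.8.12 names the same two diagnoses within a discretionary rule, and it is the section reached from the AESI list, a natural place to look once a case has been diagnosed.

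At stake are the seriousness class, the 24-hour report and the endpoint in which a case is counted. Whether the case is recorded at all is not in question, because Section 8.4.7 requires every AESI to go on the CRF as an AE or SAE.

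**Working it through.** No figure in the plan can be reproduced here. The check compares texts and adds some window arithmetic.

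**Step 1. The two rules.** Section 10.12.8.10 takes the two diagnoses out of investigator discretion and leaves discretion for the rest. Section 10.12.8.12 lists them by name inside that discretion. Reading the second alone, an investigator would not learn of the mandatory rule. It refers onward to 8.4.7, which refers back to 10.12.8.12.

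**Step 2. Precedence.** No section ranks the two. The cross-references do not imply a ranking either. The menstrual-disturbance procedures are also duplicated (10.12.8.11 and 10.12.8.13), and there 8.4.7 cites the first of the pair; for myocarditis it cites the second.

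**Step 3. Windows.**

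- AESI window (8.4.7): 6 × 7 = 42 days.
- AE endpoint (Substudy B SAP, 6.1.2.1): 4 × 7 = 28 days.
- Gap: 42 − 28 = 14 days.
- Measured by visits, AE collection ends at Visit 204 (day 26 to 30), or day 28 to 32 with the 48 hours after the blood draw. The gap is then between 42 − 32 = 10 and 42 − 26 = 16 days.
- SAEs are collected and analysed to 6 months.

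**Step 4. What follows from each classification.**

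| Onset | Classed SAE | Classed nonserious |
|---|---|---|
| Within 4 weeks | 24-hour report; in SAE endpoint; stopping rule met (Groups 2, 6–12) | No 24-hour report; in AE endpoint only; stopping rule still met (same groups) |
| After week 4, to week 6 | 24-hour report; in SAE endpoint; outside stopping-rule window | No 24-hour report; in neither endpoint; outside stopping-rule window |

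The missing 24-hour report follows from 8.4.7 and 8.4.1.1, and from the table in 10.3.3, which requires no expedited form for nonserious AEs. The stopping rule (10.12.8.7) applies within 4 weeks and is met by one confirmed diagnosis of any seriousness.

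**Step 5. Other summaries for the lower-right cell.** The cardiac-symptom summaries in the Substudy B SAP (6.4.1 and 6.5) are limited to symptoms within 4 weeks. Its AE section (6.1.2.2) names no AESI summary, whereas the Substudy A SAP does. A week-5 case classed nonserious would therefore have no named place in the planned tables.

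**The case against.** The strongest reply is that the two rules can be followed together. One is specific and mandatory, the other general, and an investigator who reports myocarditis as an SAE satisfies both. That stands. A reader might infer that the sections are impossible to reconcile in practice, but nothing in 10.12.8.12 tells anyone to class a case nonserious. The defect is an unresolved ambiguity.

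Several other safeguards also stand. The visit procedures and ECG section send sites to the strict rule. Section 10.3.2 says that significant medical events should usually count as serious. Under 8.4.1.2 the sponsor can upgrade a nonserious event, and 8.4.7 has AESIs examined in routine safety review. The risk table calls these cases very rare and says that they typically occur within 14 days of vaccination, which makes onset in weeks 4 to 6 less likely still. These points lower the probability of harm without settling which section governs: a presumption is weaker than a requirement, and a sponsor upgrade comes after the site's classification. The same risk table calls the cases generally mild, so a non-hospitalised presentation is plausible.

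A reader might also infer from the schema footnote that Groups 1, 3, 4 and 5 are outside the problem, leaving 8 × 30 = 240 of 630 participants. The footnote explains only why those groups have no sentinel pause. Both sections apply to any study participant, and the documents do not say how many were still within 6 weeks of vaccination, or yet to be vaccinated, when Amendment 6 took effect.

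**Conclusion.** The inconsistency is real and should be corrected. It concerns an operative safety-reporting rule, but its likely effect is small. Harm needs four things together: a case occurs, the site works from 10.12.8.12, the investigator judges the case nonserious, and the sponsor does not upgrade it promptly. The 24-hour report is then missing. If onset also falls in the 14 days between week 4 and week 6, the case enters neither primary AE/SAE endpoint.

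No expected number of cases can be given. One event in a group of 30 moves a proportion by 1/30 = 3.3 percentage points, but that is true of any event and does not measure this problem. Substudy B is descriptive, so no hypothesis test is affected, and no stopping decision changes. The documents do not support reading this as a route by which cases go unrecorded or the stopping rule is bypassed.

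**What to change.** Delete Section 10.12.8.12, moving its opening sentence on close monitoring into 10.12.8.10 if wanted. Deletion is the cleaner option, because 10.12.8.12 also omits the cardiology evaluation that 10.12.8.10 requires after an abnormal ECG or troponin result. If the section is kept, replace its seriousness sentence with the mandatory-SAE sentence of 10.12.8.10. Either way, make Sections 2.3.1 and 8.4.7 cite 10.12.8.10. Any diagnosed case in weeks 4 to 6 then has a 24-hour report and counts in the 6-month SAE endpoint.

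Only protocol wording changes; visits, data collection and the SAP stay as they are. Under Section 10.1.1 the amendment needs IRB/EC approval before implementation, and health authority approval if it is substantial. The amendment history classed the earlier extension of the myocarditis AESI window as substantial, so that is possible here. It is best bundled with the next amendment, when the duplicate menstrual-disturbance sections can also be merged.
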